## **7.5 Safety**

### **7.5.1 Physical examination**

A complete physical examination will be performed at Visits 1, 2, 3, and 4. It will include the examination of general appearance, skin, neck (including thyroid), eyes, ears, nose, throat, lungs, heart, abdomen, back, lymph nodes, extremities, vascular and neurological. If indicated based on medical history and/or symptoms, rectal, external genitalia, breast, and pelvic exams will be performed.

A short physical exam will include the examination of general appearance and vital signs (BP and pulse). A short physical exam will be at all visits starting from Visit 2, except where a complete physical exam is required (see above).

Information about the all physical examinations must be present in the source documentation at the study site. Significant findings that are present prior to the start of study drug must be included in the Relevant Medical History/Current Medical Conditions screen on the patient's electronic case report form. Significant findings made after the start of study drug which meet the definition of an adverse event must be recorded on the adverse event screen of the patient's electronic case report form.

### **7.5.2 Vital signs**

Vital signs will be assessed at every visit. This will include BP and pulse measurements. BP will be measured by using a standard sphygmomanometer with an appropriate size cuff and the non-dominant arm in the sitting position after 5 minutes of rest.

### **7.5.3 Height, weight, and waist/hip circumference**

Height in centimeters (cm) will be measured at Visit 1.

Body weight (to the nearest 0.1 kilogram [kg] in indoor clothing without shoes) will be measured at all visits, until the end of study visit.

Waist/hip circumference (to the nearest centimeter [cm] in indoor clothing) will be measured at Visit 2 and at the end of study visit.

### **7.5.4 Laboratory evaluations**

A central laboratory will be used for analysis of all collected specimens. Details on the collections, shipment of samples and reporting of results by the central laboratory will be provided to investigators in the laboratory manual.

Clinically notable laboratory findings are defined in Appendix 1.

Complete laboratory evaluations (hematology, blood chemistry, and urine; Table 7-2) for the assessment of safety in this study will be performed at Visits 1, 2, 3, and 4.

Laboratory values that exceed the boundaries of a notable laboratory abnormality must be commented on by the investigator in the Comments screen of the patient's electronic case report form and additional laboratory evaluations should be performed, as judged appropriate by the investigator. If the laboratory abnormality induces clinical signs or symptoms, or requires therapeutic intervention, then the diagnosis or medical condition must be entered on the adverse events screen of the patient's electronic case report form. If the laboratory abnormality is the primary reason for an unforeseen hospitalization or otherwise fulfills the seriousness category of an adverse event, then the procedure for rapid notification of serious adverse event must be followed. Likewise, if the laboratory abnormality leads to discontinuation from the study drug (temporarily or permanently), the patient must be followed until the abnormality resolves or until it is judged to be permanent. This investigation may include continued monitoring by repeat laboratory testing or by performing additional laboratory tests as deemed necessary by the investigator.

**Table 7-2 Routine laboratory examinations**

Hematology*	Biochemistry*	Urine measurements
Red Blood Cells count White Blood Cells count Platelet Count Hemoglobin Hematocrit WBC Differential	Sodium Potassium Chloride Calcium Blood urea nitrogen (BUN) Creatinine Total Bilirubin Aspartate amino-transferase (AST) Alanine amino-transferase (ALT) Alkaline phosphatase Total protein Albumin Uric Acid Serum Pregnancy Testa Lipid profile (total cholesterol, LDL, HDL, and triglycerides) Hemoglobin A1C	UACR (to calculate urinary albumin/creatinine ratio) Urinalysis

	High Sensitivity Cardiac Troponin I (Hs-cTnI)	
--	--	--

\* List of laboratory assessments performed at Visits 1, 2, 3, 4.

a. At Visit 1 and in case of positive urine pregnancy test only.

#### **7.5.4.1 Hematology**

Hemoglobin, hematocrit, red blood cell count, white blood cell count with differential, and platelet count will be measured at Visits 1, 2, 3, and 4 (Table 7-2).

#### **7.5.4.2 Clinical chemistry**

Blood urea nitrogen (BUN), glucose, creatinine, total bilirubin, AST (SGOT), ALT (SGPT), alkaline phosphatase, sodium, potassium, chloride, calcium, hemoglobin A1C, High Sensitivity Cardiac Troponin I (Hs-cTnI), total protein, albumin, uric acid, and lipid profile will be measured at Visits 1, 2, 3, and 4. Fractionated bilirubin will be performed for all patients whose total bilirubin value is > 2x ULN.

#### **7.5.4.3 Potassium and eGFR assessments**

In addition to the central laboratory assessments, potassium and eGFR, may be measured locally during the screening period (Visit 1), up to the randomization visit (Visit 2) to determine eligibility of the patient into the trial. potassium and eGFR measurements may also be performed during the outpatient dose titration and follow-up period, mainly at the unscheduled visits, to monitor the tolerability to study medication dose administered and adjust medication dose if needed.

#### **7.5.4.4 Urinalysis**

Dipstick-test determination of specific gravity, pH, blood, total protein, bilirubin, ketones, and leukocytes will be measured at Visits 1, 2, 3 and 4.

#### **7.5.5 Electrocardiogram (ECG)**

A standard 12-lead ECG will be performed at screening (Visit 1), randomization (Visit 2), Visit 3 and Visit 4. Interpretation of the tracing must be made by a qualified physician and documented on the ECG section of the electronic case report form. Each ECG tracing should be labeled with the patient initials, patient number, and date and kept in the source documents. Only clinically significant abnormalities should be reported on this page. Clinically significant abnormalities should also be recorded on the relevant medical history/current medical conditions or adverse event electronic case report form page.

### **7.5.6 Pregnancy and assessments of fertility**

All female patients of childbearing potential will have a serum pregnancy test performed at visit 1 and Visit 4. In case of a positive urine pregnancy result a confirmatory serum pregnancy test will be performed at the central laboratory. See Section 6.4.3 and Section 8.3 for details on pregnancies.

### **7.5.7 Angioedema**

Angioedema is a type of abrupt swelling that occurs under the skin and/or mucous membranes and is often localized to the head, neck, throat, and/or tongue, but may occur elsewhere, including the genitalia and intestines. Severe cases may be associated with airway compromise. Although, the mechanism is not fully understood, bradykinin has been implicated as the putative mediator. Therefore, medications that raise the levels of endogenous bradykinin by inhibiting the enzymes responsible for its breakdown, such as ACE, aminopeptidase P, and NEP, may result in this potentially dangerous side effect.

Simultaneous inhibition of multiple breakdown pathways of bradykinin is thought to significantly increase the risk of occurrence of angioedema. Section 4.2.2 details how to avoid the simultaneous inhibition of the ACE and NEP pathways by overlapping exposure to sacubitril/valsartan and enalapril at Visit 2 (randomization). The method outlined in Section 4.2.2 is expected to provide at least 36 hours free of significant simultaneous inhibition of NEP and ACE, thereby minimizing the potential risk of occurrence of angioedema. This 36-hour washout period is expected to present minimal risk to patients.

The procedure for reporting angioedema-like events is outlined in Section 8.5.

## **8 Safety monitoring**

### **8.1 Adverse events**

An AE is the appearance or worsening of any undesirable sign, symptom, or medical condition occurring after starting the study drug even if the event is not considered to be related to study drug. Study drug includes the investigational drug under evaluation and the comparator drug or placebo that is given during any phase of the study. Medical conditions/diseases present before starting study drug are only considered AEs if they worsen after starting study drug. Abnormal laboratory values or test results constitute AEs only if they induce clinical signs or symptoms, are considered clinically significant, or require therapy.

The occurrence of AEs should be sought by non-directive questioning of the patient at each visit during the study. AEs also may be detected when they are volunteered by the patient during or between visits or through physical examination, laboratory test, or other assessments.

All AEs must be recorded on the Adverse Events CRF with the following information:

1. the severity grade [mild, moderate, severe]
2. its relationship to the study drug(s) (suspected/not suspected)
3. its duration (start and end dates or if continuing at final exam)
4. whether it constitutes a serious adverse event (SAE)

An SAE is defined as an event which:

- is fatal or life-threatening
- results in persistent or significant disability/incapacity
- constitutes a congenital anomaly/birth defect
- requires inpatient hospitalization or prolongation of existing hospitalization, unless hospitalization is for:
  - routine treatment or monitoring of the studied indication, not associated with any deterioration in condition
  - elective or pre-planned treatment for a pre-existing condition that is unrelated to the indication under study and has not worsened since the start of study drug
  - treatment on an emergency outpatient basis for an event not fulfilling any of the definitions of a SAE given above and not resulting in hospital admission
  - social reasons and respite care in the absence of any deterioration in the patient's general condition
- is medically significant, i.e. defined as an event that jeopardizes the patient or may require medical or surgical intervention to prevent one of the outcomes listed above.

**Unlike routine safety assessments, SAEs are monitored continuously and have special reporting requirements; see Section 8.2.**

All AEs should be treated appropriately. Treatment may include one or more of the following: no action taken (i.e. further observation only); study drug dosage adjusted/temporarily interrupted; study drug permanently discontinued due to this AE; concomitant medication given; non-drug therapy given; patient hospitalized/patient's hospitalization prolonged. The action taken to treat the AE should be recorded on the Adverse Event Case Record Form.

Once an AE is detected, it should be followed until its resolution or until it is judged to be permanent, and assessment should be made at each visit (or more frequently, if necessary) of any changes in severity, the suspected relationship to the study drug, the interventions required to treat it, and the outcome.

Information about common side effects already known about the investigational drug can be found in the Drug Instructions. This information will be included in the patient informed consent and should be discussed with the patient during the study as needed.

## **8.2 Serious adverse event reporting**

To ensure patient safety, every SAE, regardless of suspected causality, occurring after the patient has provided informed consent and until 30 days after the patient has stopped study participation must be reported to research team within 24 hours of learning of its occurrence.

Any SAEs experienced after this 30 days period should only be reported to research team if the investigator suspects a causal relationship to the study drug.

Recurrent episodes, complications, or progression of the initial SAE must be reported as follow-up to the original episode, regardless of when the event occurs. This report must be submitted within 24 hours of the investigator receiving the follow-up information. An SAE that is considered completely unrelated to a previously reported one should be reported separately as a new event.

Information about all SAEs is collected and recorded on the Serious Adverse Event Report Form. The investigator must assess the relationship to study drug, complete the SAE Report Form in English. The original copy of the SAE Report Form must be kept with the case report form documentation at the study site.

Follow-up information is sent to the same person to whom the original SAE Report Form was sent, using a new SAE Report Form stating that this is a follow-up to the previously reported SAE and giving the date of the original report. The follow-up information should describe whether the event has resolved or continues, if and how it was treated, and whether the patient continued or withdrew from study participation.

## **8.3 Pregnancies**

In case a patient becomes pregnant, or plans to become pregnant, the study drug must be interrupted before contraception is discontinued (or, from the date the pregnancy becomes known) for the entire duration of the pregnancy and lactation period (or, for the entire duration that contraception is discontinued). To ensure patient safety, each pregnancy in a patient on study drug must be reported to research team within 24 hours of learning of its occurrence. The pregnancy should be followed up to determine outcome, including spontaneous or voluntary termination, details of the birth, and the presence or absence of any birth defects, congenital abnormalities, or maternal and/or newborn complications.

Pregnancy should be recorded on a Clinical Trial Pregnancy Form and reported by the investigator to the research team. Pregnancy follow-up should be recorded on the same form and should include an assessment of the possible relationship to the study drug of any pregnancy outcome. Any SAE experienced during pregnancy must be reported on the SAE Report Form.

#### **8.4 Data Monitoring Committee**

An external data monitoring committee (DMC) independent of research team will be appointed to monitor the study conduct. Any major recommendation from the DMC will be communicated to the research team and must be reviewed and ratified by the research team prior to its enactment.

#### **8.5 Reporting angioedema-like events**

It is important that the investigator pays special attention to any swelling or edema that may resemble angioedema or angioedema-like events that may be reported by patients. If such an event occurs, the investigator will complete an Adjudication Questionnaire for an Angioedema-like Event form (provided by research team) to summarize the event, its treatment, and its ultimate outcome and communicate this report to research team as soon as possible. Follow-up reports must be communicated to research team as soon as new information regarding the event becomes available.

Occasionally, the investigator may be contacted by the research team regarding AEs that were reported on behalf of patients that may resemble an angioedema-like event. The investigator or his/her delegated staff must complete the required report forms and supply the required medical records for such events, regardless of whether the investigator views the event in question as angioedema or not. All angioedema reports will be forwarded to research team for assessment.

Submission of an angioedema report is not a substitution for the submission of a SAE report. If an angioedema-like event satisfies the definition of a SAE, the investigator must submit a SAE report (as described in Section 8.2) in addition to the Adjudication Questionnaire for an Angioedema-like Event

## **9 Data review and database management**

### **9.1 monitoring**

Before study initiation, at an investigator s meeting, research team will review the protocol and electronic case report forms. During the study, the monitor will visit the database regularly to check the completeness of patient records, the accuracy of entries on the electronic case report forms, the adherence to the protocol and to Good Clinical Practice, the progress of enrollment. Key study personnel must be available to assist the field monitor during these visits.

The investigator must maintain source documents for each patient in the study, consisting of case and visit notes (hospital or clinic medical records) containing demographic and medical information, laboratory data, electrocardiograms, and the results of any other tests or assessments. All information on electronic case report forms must be traceable to these source documents in the patient's file. Data not requiring a separate written record will be defined before study start and will be recorded directly on the case report forms. The investigator must also keep the original informed consent form signed by the patient (a signed copy is given to the patient).

The investigator must maintain source documents for each patient in the study, consisting of case and visit notes (hospital or clinic medical records) containing demographic and medical information, laboratory data, electrocardiograms, and the results of any other tests or assessments. All information on eCRFs must be traceable to these source documents in the patient's file. Data not requiring a separate written record will be defined before study start and will be recorded directly on the CRFs. The investigator must also keep the original informed consent form signed by the patient (a signed copy is given to the patient).

### **9.2 Data collection**

Designated investigator staff will enter the data required by the protocol into the Electronic Case Report Forms. The Investigator must certify that the data entered into the Electronic Case Report Forms are complete and accurate.

### **9.3 Database management and quality control**

The research team reviews the data entered into the electronic case report forms by investigational staff for completeness and accuracy and instruct the investigator to

make any required corrections or additions. Obvious errors are corrected by research team.

## **10 Data analysis**

### **10.1 Populations for analysis**

The full analysis set (FAS) will consist of all randomized patients. Following the intent-to-treat principle, patients will be analyzed according to the treatment to which they were assigned at randomization. Efficacy variables will be analyzed based on the FAS as the primary population.

### **10.2 Patient demographics/other baseline characteristics**

Baseline value is defined as the last non-missing assessment prior to the first dose of randomized study medication unless specified otherwise. Summary statistics will be provided by treatment group for demographics and baseline characteristics, including age, sex, weight, height, body mass index (BMI), Previous history of hypertension, prior history of Diabetes mellitus, Previous smoking history, Killip class, blood tests, Number of diseased vessels, vital signs, etc. BMI will be calculated as  $\text{weight (kg)} / \text{height}^2 \text{ (m}^2\text{)}$  from the collected height and weight at Visit 1 (Screening Visit). Continuous variables will be summarized using n, mean, standard deviation, geometric mean and 95% confidence interval. Categorical variables will be summarized using frequency and percentage.

The difference between treatment groups will be compared using the Fisher's exact test for categorical variables or using t-test or Mann-Whitney U test for continuous variables. The p-values will be provided for descriptive purposes and will not be considered to define any formal basis for determining factors to be included in statistical models.

### **10.3 Analysis of the primary objective**

The primary objective of this study is to test if sacubitril/valsartan is superior to enalapril in reducing the concentration of NT-proBNP and improving the main cardiac ultrasound parameters in patients with acute anterior STEMI after PCI.

#### **10.3.1 Primary efficacy variable**

The primary efficacy outcomes are the changes in NT-proBNP concentrations from baseline through weeks 4, 12 and 24 and in echocardiographic parameters (LVEF, LVEDV, LVESV) from baseline through weeks 12 and 24.

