**Safety assessments:**

- AEs and SAEs
- hypotension
- Angioedema
- Laboratory values
- Hyperkalemia

**Data analysis:** Analyses of the change from baseline in NT-proBNP and echocardiographic parameter was performed using an analysis-of-covariance model adjusted for baseline values. Logarithmic transformation is used for NT-proBNP, due to its skewed distribution.

The secondary efficacy variables will be analyzed using Kaplan-Meier estimates and Cox proportional hazards models. The hazard ratios, 95% confidence intervals, and two-sided P values are calculated using the model to adjust the following baseline prognostic factors: Age, gender, body mass index, total cholesterol, triglycerides, history of hypertension, diabetes and Previous smoking.

We will use Fisher's exact test to compare rates of Safety outcomes.

The targeted sample size mainly is driven by the LVEF of the primary composite endpoint. Assuming that the increase in LVEF is  $3\% \pm 6\%$ , the patients are included in the ratio 1:1 when  $\alpha=0.05$  and the test power is 80%, and the sample size for each group is predicted to be 64 cases.

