## **1 Background**

Angiotensin receptor-neprilysin inhibitor (ARNI, Sacubitril/Valsartan) is superior to angiotensin-converting enzyme inhibitors (ACEI) on cardiac remodeling in patients with heart failure (HF). However, there is little data describing the effects of sacubitril/valsartan in patients with acute anterior ST-segment elevation myocardial infarction (STEMI). The objective is to assess the safety and efficacy of sacubitril/valsartan compared with Enalapril in patients with acute anterior STEMI after PCI.

This study is a single center, prospective, randomized, double-blind trial, planning to recruit patients with acute anterior STEMI at the Second Affiliated Hospital of Nanchang University. Patients are randomly assigned 1:1 to in-hospital initiation of sacubitril/valsartan and enalapril. The starting dose during the in-hospital initiation phase and all subsequent dose changes during the titration period is selected using a dose titration algorithm (Figure 1). Patients are followed up at 4, 12, and 24 weeks after discharge from the hospital, blood test and echocardiograph are performed. The primary efficacy outcomes are the changes in NT-proBNP concentrations and in echocardiographic parameters (LVEF, LVEDV, LVESV) from baseline through weeks 4, 12 and 24. Secondary outcomes include the incidence of a composite of death, reinfarction, hospitalization for heart failure or outpatient heart failure, arrhythmia, stroke. Safety endpoints are the incidence of angioedema, hypotension, renal insufficiency, and hyperkalemia.

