## **3 Study goals and objectives**

### **3.1 Primary objective:**

The primary objective of this study is to test if sacubitril/valsartan is superior to enalapril in reducing the concentration of NT-proBNP and improving the main cardiac ultrasound parameters in patients with acute anterior STEMI after PCI.

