### **4.1 Justification of key elements of the study design**

#### **4.1.1 Selection of the primary endpoint**

We chose NT-proBNP as the primary endpoint in this study because natriuretic peptide concentrations are associated with adverse outcomes in patients with AMI. Although both ANP and BNP undergo degradation by neprilysin, the biologically inert NTproBNP, cleaved from proBNP along with BNP, is not a substrate for neprilysin degradation, and changes in this marker still reflect reduction in left ventricular wall stress even in the setting of neprilysin inhibition.

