## **7.4 Efficacy**

### **7.4.1 Primary and secondary efficacy outcomes**

The primary outcomes are:

- NT-proBNP
- LVEF
- LVEDV
- LVESV

The secondary composite outcome consists of the following components:

- Death
- Reinfarction
- hospitalization for heart failure or outpatient heart failure
- arrhythmia
- stroke

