## **10.6 Sample size calculation**

The targeted sample size mainly is driven by the LVEF of the primary outcomes. Assuming that the increase in LVEF is  $3\% \pm 6\%$ , the patients are included in the ratio 1:1 when  $\alpha=0.05$  and the test power is 80%, and the sample size for each group is predicted to be 64 cases. Taking into account the loss to follow-up rate of 10%, it is estimated that a total of 142 patients will be needed

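### The protocol states its primary endpoint inconsistently, and the alpha of 0.05 and power of 80% in Section 10.6 belong to a single LVEF comparison, not to the primary objective as written

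*Protocol*

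**What the plan says.** The protocol describes what is primary in several places, and they differ.

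- **Section 4.1.1** gives the rationale for one variable: "We chose NT-proBNP as the primary endpoint in this study".
- **Section 7.4.1** opens with "The primary outcomes are" and lists NT-proBNP, LVEF, LVEDV and LVESV without a visit. The synopsis list of primary assessments has the same four.
- **Section 10.3.1** adds visits: "The primary efficacy outcomes are the changes in NT-proBNP concentrations from baseline through weeks 4, 12 and 24 and in echocardiographic parameters". NT-proBNP has three visits; the echo part reads "in echocardiographic parameters (LVEF, LVEDV, LVESV) from baseline through weeks 12 and 24".
- **Section 1** has "in echocardiographic parameters (LVEF, LVEDV, LVESV) from baseline through weeks 4, 12 and 24", a third echo visit. Section 7.4.5 schedules follow-up echo at weeks 12 and 24 only.
- **Synopsis, data analysis:** "The targeted sample size mainly is driven by the LVEF of the primary composite endpoint". The parallel sentence in **Section 10.6** is "The targeted sample size mainly is driven by the LVEF of the primary outcomes". The only composite the protocol defines is the secondary clinical one.
- **Section 3.1** asks whether sacubitril/valsartan is "superior to enalapril in reducing the concentration of NT-proBNP and improving the main cardiac ultrasound parameters".

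Section 10.3.2 specifies a baseline-adjusted ANCOVA. It names no primary visit and no success rule. Alpha of 0.05 and power of 80% appear only in the sample size text (synopsis and 10.6).

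**The concern.** A confirmatory trial needs one fixed answer to the question of which result, at which visit, decides success. Here a claim resting on NT-proBNP, on LVEF or on a ventricular volume could each point to supporting text, at more than one visit. The error rate and power of the primary objective depend on which reading applies. The sample size section quotes 0.05 and 80% for one variable only, so a reader who takes those figures as properties of the whole primary objective is misled about one or the other.

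**Working it through.** **Inputs from the protocol (10.6).** LVEF increase 3 points, SD 6 points, alpha 0.05, power 80%, 1:1 allocation, 64 per group, 10% loss, 142 in total. I read the 3 points as a between-group difference and the test as two-sided; 10.6 says neither.

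**Step 1: reproduce the stated size.**
- Normal approximation: n = 2(z₀.₉₇₅ + z₀.₈₀)² × SD²/δ² = 2 × (1.960 + 0.842)² × 36/9 = 62.8, so 63 per group.
- Exact two-sample t-test: 63 gives 79.5% and 64 gives 80.1%, so 64 per group. A one-sided test would give 50, which does not fit.
- Loss: 2 × 64 / 0.9 = 142.2, against 142 stated.

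The arithmetic is right for one two-sided LVEF comparison.

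**Step 2: count the comparisons.**
- 10.3.1: NT-proBNP × 3 visits + 3 echo variables × 2 visits = 9.
- Section 1: 4 variables × 3 visits = 12.

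**Step 3: any success counts, no correction.** Assumptions: each comparison is a separate test at 0.05, and test statistics are equally correlated (the protocol gives no correlations). If independent, familywise error = 1 − 0.95⁹ = 37.0%. With correlation, by simulation. The last column also assumes 80% power for every comparison.

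| Assumed correlation | Familywise error, 9 tests | Power for at least one win |
|---|---|---|
| 0 | 37.0% | about 100% |
| 0.5 | 26.9% | 99.1% |
| 0.8 | 16.6% | 94.7% |
| 0.9 | 12.3% | 91.3% |

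Alpha fails and power does not. With the twelve comparisons of Section 1 the error runs from 46.0% down to 13.6%.

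**Step 4: all four variables must succeed at one visit.** Assumption: each has 80% power. Alpha stays at or below 0.05. Joint power if independent = 0.8⁴ = 41.0%; by simulation it is 55.6% at correlation 0.5, 65.7% at 0.8 and 70.3% at 0.9. Alpha holds and power fails.

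**Step 5: Bonferroni over the four variables.** Each test is at 0.05/4 = 0.0125. With 64 per group, LVEF power by unadjusted t-test is 61.6% (63.0% by normal approximation). Keeping 80% for LVEF would take 90–91 per group, or 2 × 90/0.9 = 200 to 2 × 91/0.9 ≈ 203 patients. The chance of at least one success was not calculated for this rule; what is lost is the 80% stated for LVEF.

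**The case against.** **What can fairly be said on the other side.** Section 10.6 claims 80% power only for LVEF, says LVEF mainly drives the size and acknowledges several primary outcomes; it promises nothing for the whole objective, and its arithmetic is correct. The protocol sets no per-test level, and a multiplicity rule may sit in a statistical analysis plan that is not shown. The composite in the synopsis may be a slip, since 10.6 uses the plural outcomes. The magnitudes rest on assumed correlations; independence is unrealistic when LVEF derives from the two volumes and visits repeat within patients. The 62% ignores any gain from baseline adjustment. Nine comparisons presumes a separate test at each visit.

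Most of this stands, and it rules out several stronger readings that a reader might infer:

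- *Neither 0.05 nor 80% holds.* Not so under either uncorrected rule. Any-win breaks alpha but keeps power for at least one win above 80%. All-must-win, which the word and in the objective suggests, keeps alpha and breaks power.
- *Every comparison is tested at 0.05.* This is an inference; the protocol gives 0.05 only in its sample size text.
- *The primary claim will be chosen after the data are seen.* The text leaves that open, but an analysis plan could close it.
- *Sizing on LVEF is a further definition of the endpoint.* It is not; it is compatible with a list of four outcomes.

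What does not stand is the appeal to an unseen plan as a full answer. Naming the primary variable and visit is a protocol matter. Section 4.1.1 conflicts with 7.4.1 and 10.3.1, the synopsis with 10.6, and Section 1 with 7.4.5 and 10.3.1. A later plan could only overrule some of these.

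**Conclusion.** Wrong as written. The primary endpoint is given as NT-proBNP alone, as four outcomes and as an undefined composite, with two different echo schedules. The 0.05 and 80% are sound for one LVEF comparison at an unstated visit, but they cannot both hold for the primary objective as written. The size depends on the unstated rule: familywise error of about 12–37% if any of nine comparisons counts, joint power of about 41–70% if all four must succeed at one visit, or about 62% power for LVEF under Bonferroni over four. The first two ranges assume equal correlations from 0.9 to 0; the first also assumes uncorrected tests at 0.05, and the second 80% power for each variable. The 62% assumes an unadjusted t-test. The contradictions in the text need none of these assumptions.

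**What to change.** Name one primary variable at one visit. Change in LVEF at week 24, tested two-sided at 0.05, fits the variable 10.6 is sized on and needs no extra patients. Week 24 is a proposal, since 10.6 gives no visit; say there that the 80% refers to this test. Make the other variables and visits secondary; one option is a pre-specified fixed order at week 24, each tested only if the one before succeeds.

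If the sponsor prefers NT-proBNP, as 4.1.1 suggests, or all four, state the success rule and restate in 10.6 the power that 64 per group gives for that choice. For NT-proBNP the sponsor would have to supply an effect and SD, which the protocol does not give.

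Align the synopsis and Sections 1, 3.1, 4.1.1, 7.4.1, 7.4.5, 10.3 and 10.6, including the echo visits, and delete the word composite from the synopsis sample size sentence.

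Cost: with the LVEF option, a wording amendment. The small downside is that claims on the demoted variables become secondary or conditional.
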